#### 11.1.5.1 Insufficient Data for Analysis/Presentation

If there are no values/event at the general value then the break out should not be presented. For example if the number of related AEs is zero then no presentation by severity of related events at the single level will be produced.

Some of the TFLs may not have sufficient numbers of subjects or data for presentation. If this occurs, the blank TFL shell will be presented with a message printed in the center of the table, such as, “No serious adverse events occurred for this study.”

Stratified summaries by sex, or nicotine levels will not be presented if less than 4 subjects are available in one sex or nicotine levels strata. Stratified summaries by race will present only race categories with at least 4 subjects available, the remaining will be included in the “other race” category.

#### 11.1.6 Handling of Unplanned Data

Unscheduled post-product use assessments will be excluded from the summary statistics. Unscheduled assessments will be labelled as unscheduled in the listings and mapped to the study day using the date of the study day until midnight.

#### 11.1.7 Multiple Comparisons / Multiplicity

No formal adjustment of the test-wise alpha level for multiple testing is necessary, as the primary definition of success includes is the precision of the estimates of the primary endpoint and no claim(s) will be made based on the outcome of the individual tests.

### 11.2 Disposition of Subjects

The number and percent of subjects will be summarized for the following categories: subjects screened, screening failures that tried product, screening failures that did not try product, enrolled subjects, enrolled and not randomized, randomized subjects, completed, and discontinued (if applicable discontinued subject that never used their allocated products will be identified).

Inclusion and exclusion criteria will be listed as to whether the subjects have met or not met the criteria by sequence, subject and study day (Screening and Admission).

Subjects in the Safety and PK populations will be displayed by sequence and overall.

All subjects who fail to complete the study will be categorized by their primary reason for discontinuation and summarized by sequence and overall. Disposition of subjects and reasons for withdrawal will also be summarized separately. Supportive listings will be provided.

The number and percent of randomized subjects with protocol deviations and the number of protocol deviations will be summarized by sequence and overall, broken down by main deviation category (major/minor) and sub-categories. Subjects will be counted once per deviation category, and can be counted for more than one deviation category.

Supportive listing will be provided, including any additional comments for tests that are not performed to be included on the listings of individual data.

The data will be presented in the below outputs:

TFL number	Title
TABLES	
15.2.1.1	Summary of Subject Disposition – All Screened Subjects
15.2.1.2	Summary of Reasons for Discontinuations – All Randomized Subjects
15.2.1.3	Summary of Protocol Deviations – Safety Population
LISTINGS	
15.3.1.1	Listing of Inclusion/Exclusion Criteria
15.3.1.8	Listing of Subject Disposition and Assignment to Analysis Sets
15.3.1.13	Listing of Protocol Deviations
15.3.2.7	Listing of Subjects and Observations Excluded from Efficacy Analysis
16.1.7	Listing of Randomization Scheme and Codes

### 11.3 Demographics and Other Baseline Characteristics

Demographic and baseline characteristics will be summarized for the Safety and PK populations, and listed for the Safety population.

The demographic variables age, sex, race, body weight, height and BMI will be summarized by sequence and overall for the Safety population.

Demographics will be tabulated overall and by the two stratification factors (sex and mCC nicotine level at Admission) for the PK populations, as specified in Section 11.1.1 “Stratified Presentation”.

No inferential analyses will be presented for the demographic and baseline characteristics.

The data will be presented in the below outputs:

TFL number	Title
TABLES	
15.2.1.4.1	Summary of Demographics and Other Baseline Characteristics – Safety Population
15.2.1.4.2	Summary of Demographics and Other Baseline Characteristics – Group-1 PK Population
15.2.1.4.2.1	Summary of Demographics and Other Baseline Characteristics by Sex – Group-1 PK Population
15.2.1.4.2.2	Summary of Demographics and Other Baseline Characteristics by Nicotine Level – Group-1 PK Population
15.2.1.4.3	Summary of Demographics and Other Baseline Characteristics – Group-2 PK Population
15.2.1.4.3.1	Summary of Demographics and Other Baseline Characteristics by Sex – Group-2 PK Population
15.2.1.4.3.2	Summary of Demographics and Other Baseline Characteristics by Nicotine Level – Group-2 PK Population
LISTINGS	
15.3.1.7	Listing of Demographics

### 11.3.1 CYP2A6 Activity at Admission

CYP2A6 activity will be calculated as the metabolic ratio of trans 3' hydroxycotinine and cotinine measured at Day -1, as described in Section 7.2.1 “CYP2A6”. Data will be listed and summarized as reported in Section 11.3 “Demographics and Other Baseline Characteristics”.

The data will be presented in the below outputs:

TFL number	Title
TABLES	
15.2.1.4.1	Summary of Demographics and Other Baseline Characteristics – Safety Population
15.2.1.4.2	Summary of Demographics and Other Baseline Characteristics – Group-1 PK Population
15.2.1.4.2.1	Summary of Demographics and Other Baseline Characteristics by Sex – Group-1 PK Population
15.2.1.4.2.2	Summary of Demographics and Other Baseline Characteristics by Nicotine Level – Group-1 PK Population
15.2.1.4.3	Summary of Demographics and Other Baseline Characteristics – Group-2 PK Population
15.2.1.4.3.1	Summary of Demographics and Other Baseline Characteristics by Sex – Group-2 PK Population
15.2.1.4.3.2	Summary of Demographics and Other Baseline Characteristics by Nicotine Level – Group-2 PK Population

TFL number	Title
LISTINGS	
15.3.1.12	Listing of CYP2A6 Activity

### 11.3.2 FTND Questionnaire at Screening

FTND score value and the number and percentage of subjects in each category (mild/moderate/severe) will be presented. Data will be listed and summarized as reported in Section 11.3 “Demographics and Other Baseline Characteristics”.

The data will be presented in the below outputs:

TFL number	Title
TABLES	
15.2.1.4.1	Summary of Demographics and Other Baseline Characteristics – Safety Population
15.2.1.4.2	Summary of Demographics and Other Baseline Characteristics – Group-1 PK Population
15.2.1.4.2.1	Summary of Demographics and Other Baseline Characteristics by Sex – Group-1 PK Population
15.2.1.4.2.2	Summary of Demographics and Other Baseline Characteristics by Nicotine Level – Group-1 PK Population
15.2.1.4.3	Summary of Demographics and Other Baseline Characteristics – Group-2 PK Population
15.2.1.4.3.1	Summary of Demographics and Other Baseline Characteristics by Sex – Group-2 PK Population
15.2.1.4.3.2	Summary of Demographics and Other Baseline Characteristics by Nicotine Level – Group-2 PK Population
LISTINGS	
15.3.1.11	Listing of Fagerström Test for Nicotine Dependence Results

### 11.3.3 Current Cigarette and Smoking Characteristics

The following smoking characteristics at Admission (Day -1) will be summarized and listed as specified in Section 11.3 “Demographics and Other Baseline Characteristics”: ISO tar yield (continuous and categorized as 1-5 mg, 6-8 mg, 9-10 mg and >10 mg), ISO nicotine level (continuous and categorized as ≤1 mg and > 1 mg), and number of mCCs smoked on a daily basis during the previous 4 weeks (categorized as < 10 cig/day, 10-19 cig/day and >19 cig/day).

Current mCC brand(s) smoked by the subject and recorded at Admission (Day -1) will be summarized and listed by sequence and study day for the safety population. This will include brand name(s), ISO nicotine and tar yields. The smoking characteristics and current mCC brand collected at Screening Visit will be listed only.

Smoking history, including whether subjects have smoked for at least the last three consecutive years and whether the subject smoked any non-menthol CCs during the previous 4 weeks will be listed by sequence at Screening and Admission (Day -1) where applicable. Responses to planning to quit smoking during the next 3 months will be listed at Screening. Willingness to use the product will be listed at Admission.

Data will be listed and summarized as presented in the below outputs:

TFL number	Title
TABLES	
15.2.1.4.1	Summary of Demographics and Other Baseline Characteristics – Safety Population
15.2.1.4.2	Summary of Demographics and Other Baseline Characteristics – Group-1 PK Population
15.2.1.4.2.1	Summary of Demographics and Other Baseline Characteristics by Sex – Group-1 PK Population
15.2.1.4.2.2	Summary of Demographics and Other Baseline Characteristics by Nicotine Level – Group-1 PK Population
15.2.1.4.3	Summary of Demographics and Other Baseline Characteristics – Group-2 PK Population
15.2.1.4.3.1	Summary of Demographics and Other Baseline Characteristics by Sex – Group-2 PK Population
15.2.1.4.3.2	Summary of Demographics and Other Baseline Characteristics by Nicotine Level – Group-2 PK Population
15.2.1.5	Summary of Current Cigarette Brands at Admission – Safety Population
LISTINGS	
15.3.1.2	Listing of Current Cigarette Brands
15.3.1.3	Listing of Smoking History
15.3.1.5	Listing of Product Test Willingness to Use the Product, Willingness to Quit Smoking

#### 11.3.4 Socio-Economic Status Questionnaire

Subject answers, individual educational attainment, annual household income and composite classifications will be listed. The number and percentage of subjects in each of the socio-economic status gradings will also be summarized as reported in Section 11.3 “Demographics and Other Baseline Characteristics”, and presented in listings as shown below:

TFL number	Title
TABLES	
15.2.1.4.1	Summary of Demographics and Other Baseline Characteristics – Safety Population

TFL number	Title
15.2.1.4.2	Summary of Demographics and Other Baseline Characteristics – Group-1 PK Population
15.2.1.4.2.1	Summary of Demographics and Other Baseline Characteristics by Sex – Group-1 PK Population
15.2.1.4.2.2	Summary of Demographics and Other Baseline Characteristics by Nicotine Level – Group-1 PK Population
15.2.1.4.3	Summary of Demographics and Other Baseline Characteristics – Group-2 PK Population
15.2.1.4.3.1	Summary of Demographics and Other Baseline Characteristics by Sex – Group-2 PK Population
15.2.1.4.3.2	Summary of Demographics and Other Baseline Characteristics by Nicotine Level – Group-2 PK Population
LISTINGS	
15.3.1.9	Listing of Socio-Economic Questionnaire Results

### 11.3.5 Medical History and Concomitant Diseases

Medical history is defined as any condition that started and ended prior to Screening. Medical history will be coded using Medical Dictionary for Regulatory Activities (MedDRA) version 16.0 and listed separately by sequence, System Organ Class (SOC) and Preferred Term (PT) within SOC.

Concomitant disease is defined as any condition diagnosed at Screening or was ongoing at Screening. Concomitant disease will be coded using MedDRA version 16.0 and listed separately by sequence, SOC and PT within SOC.

Partial dates will not be imputed, but assumptions will be made as follows to assign to either medical history or concomitant diseases:

Date information	Assign as
Missing stop date	Concomitant disease
Partial date, e.g., --May2012, or ----2011. If month/year is the same as, or later than the month and/or year of Screening.	Concomitant disease
Partial date, e.g., --May2012, or ----2011. If month and/or year is earlier than the month and/or year of Screening.	Medical history

The data will be presented in the below outputs:

TFL number	Title
TABLES	
15.2.1.6	Summary of Medical History – Safety Population

TFL number	Title
15.2.1.7	Summary of Concomitant Diseases – Safety Population
LISTINGS	
15.3.1.10	Listing of Medical History and Concomitant Disease

### 11.3.6 Other Data

Other data collected at Screening and/or Admission will be listed by sequence and subject. These data are as follows:

- Cotinine urine test
- Urine pregnancy test
- Chest x-ray
- Urine drug screen
- Serology
- Alcohol breath test
- Prior medication
- Product Test and Demonstration
- Identification of NNS brand
- Willingness to use THS 2.2 Menthol and NNS products

Willingness and ability to use the products will also be summarized.

The data will be presented in the below outputs:

TFL number	Title
TABLES	
15.2.1.1	Summary of Subject Disposition – All Screened Subjects
LISTINGS	
15.3.1.5	Listing of Product Test Willingness to Use the Product, Willingness to Quit Smoking, Readiness to Accept Smoking Interruption
15.3.1.6	Listing of Safety Laboratory Entry Criteria
15.3.6.3	Listing of Prior and Concomitant Medication

### 11.4 Measurements of Product Compliance

Levels of CO in exhaled breath will be measured to evaluate the exposure to CO (see Section 11.6.2.2.1 “Exhaled CO and COHb”), and to monitor compliance during the following study days (see Section 6.3.3 “Compliance to Product Allocation”):

- Wash-out on Day 0 and Day 2
- Single use Day 1 and Day 3 for subjects exposed to NNS.

CO data will be listed and summarized by sequence for all study days and timepoints as continuous variable and with the categorization  $\leq 10$  ppm and  $> 10$  ppm.

Values above 10 ppm will be highlighted in listings and be considered as non compliance if such values are observed prior to first product use on the single use days for all exposures and throughout the single use days for NNS exposure. During the washout days values above 10 ppm will be considered non-compliance on Day 2, but will be expected on Day 0 because smoking is ad libitum during Day -1. CO data leading to exclusion of subjects from the analysis will be evaluated during the pre-analysis blind data review.

Number and percentage of subjects considered as non compliant during the study will be tabulated by sequence and study days for all randomized subjects.

The data will be presented in the below outputs:

TFL number	Title
<hr/>	
TABLES	
15.2.4.10.1	Descriptive Statistics of Exhaled CO (ppm) During Single Use Continuous Measurements – PK Population
15.2.4.10.1.1	Descriptive Statistics of Exhaled CO (ppm) During Single Use by Sex – PK Population
15.2.4.10.1.2	Descriptive Statistics of Exhaled CO (ppm) During Single Use by Nicotine Level – PK Population
15.2.4.10.2	Descriptive Statistics of Exhaled CO (ppm) During Single Use Categorical Measurements – PK Population
15.2.4.11.1	Descriptive Statistics of Exhaled CO (ppm) During Days -1, 0, 2 and 4 Continuous Measurements – PK Population
15.2.4.11.1.1	Descriptive Statistics of Exhaled CO (ppm) During Days -1, 0, 2 and 4 by Sex – PK Population
15.2.4.11.1.2	Descriptive Statistics of Exhaled CO (ppm) During Days -1, 0, 2 and 4 by Nicotine Level – PK Population
15.2.4.11.2	Descriptive Statistics of Exhaled CO (ppm) During Days -1, 0, 2 and 4 Categorical Measurements – PK Population
15.2.5.1	Descriptive Statistics of Compliance – All Randomized Subjects
LISTINGS	
15.3.3.5	Listing of Exhaled Breath CO (ppm) and Measurement Times

---

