6.3.2 Investigational Period (Day 0 to Day 3)

During the first washout, each subject will maintain nicotine abstinence from Day -1 at 11:00 PM to the time of single use of his/her allocated product at Day 1. At Day 1, after the single use of the product, subjects will maintain nicotine abstinence for the rest of the day. During the second washout on Day 2, subjects will maintain nicotine abstinence until the time of single use of his allocated product at Day 3. Subjects will not be allowed to smoke or use any other nicotine/tobacco-containing products other than the products they are allocated to.

Time point 0 will be defined as start of the single product use on the single use days or as start of the first product use on each study day. The start of product use for THS 2.2 Menthol is defined as the time of the first puff. The start time for mCC corresponds to the lighting of the mCC, and the start time of the product is the time of the spray in the first nostril. The 30 seconds it takes to pre-heat the tobacco stick holder will not be taken into account. **The subject must not take a puff of the tobacco stick during the pre-heating time.**

The start of the first product use can be different for each subject both days of product use. However, it must be in the window of 6:00 AM to 9:00 AM.

Confidentiality Statement: Data and information contained in this document are considered to constitute trade secrets and confidential commercial information, and the legal protections provided to such trade secrets and confidential information are hereby claimed under the applicable provisions of United States law. No part of this document may be publicly disclosed without the written consent of Philip Morris International.

Single use of products (Day 1 and Day 3)

On Day 1 and Day 3, subjects will use the product they are randomized to only once in the morning between 6:00 AM to 9:00 AM, and will abstain from the product or other nicotine/tobacco-containing items for the rest of the day, i.e., subjects in the THS 2.2 Menthol arm will use one Menthol Tobacco Stick, subjects in the mCC arm will smoke one mCC, and subjects in the NNS arm will spray once into each nostril (leading to an estimated total administered amount of 1 mg nicotine), as shown:

	Sequence 1	Sequence 2	Sequence 3	Sequence 4
Day 1	THS 2.2 Menthol	mCC	THS 2.2 Menthol	NNS
Day 3	mCC	THS 2.2 Menthol	NNS	THS 2.2 Menthol

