6.6.4 Compliance to Investigational Products

Compliance for all arms will be ensured by strict distribution of the products (product by product) and collection of used Tobacco Sticks, the CC butts and the NNS after use will be documented in appropriate logs.

In addition, in subjects using NNS, the compliance will be chemically verified using exhaled CO breath. The cut-off point for the CO breath test value to distinguish tobacco use vs. no tobacco use will be 10 ppm (Beal, 1989).

Furthermore, the CO breath test will be considered as one of the measures of compliance during the wash-out days in all subjects.

Confidentiality Statement: Data and information contained in this document are considered to constitute trade secrets and confidential commercial information, and the legal protections provided to such trade secrets and confidential information are hereby claimed under the applicable provisions of United States law. No part of this document may be publicly disclosed without the written consent of Philip Morris International.

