#### 3.1 Revision History

Version	Date of Revision	Revision
3.0	23 April 2014	

• For a number of subjects the nicotine concentrations at <math>T_0</math> were higher than expected, therefore the statistical analyses were updated to accommodate this finding:

1) The primary analysis was updated to include all subjects irrespective of their <math>T_0</math>.

2) The originally planned analysis (SAP v1.0) became a supportive analysis (excluding subjects based on the concentrations their <math>T_0</math> with respect to their <math>C_{max}</math>).

• Clarification of the analysis of the Cotinine data that is specified in the protocol.

Version	Date of Revision	Revision
		

• Listing on the advise of risk of smoking will not be produced as data will not be available in the analysis data sets.

• Clarification that data collected at discharge visit will be presented at Day 4/Discharge.

• The document Revision History was added to the SAP.

2.0	18 December 2013	

• The SAP was updated to incorporate a number of minor changes across different document sections, including fixing of typos, re-wording and text format, TFL numbers and titles, and the specification of the following statistical analysis methods.

• Data handling methods and sensitivity analysis were expanded to address missing time data for <math>T_0</math> and PK assessment timepoints.

• A sensitivity analysis using bootstrap technique for the evaluation of the MCEQ domain scores was added.

1.0	23 August 2013	Original SAP

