### 6.3.3 Compliance to Product Allocation

Compliance will be ensured by strict distribution of the products (product by product) and collection of used Menthol Tobacco Sticks, the mCC butts and/or the NNS after each use. This information will be documented in appropriate logs.

In addition, in subjects using NNS, the compliance will be chemically verified using exhaled CO breath. The cut-off point for the CO breath test value to distinguish tobacco use vs. no tobacco use will be 10 ppm (Bennowitz et al, 2002).

Furthermore, the CO breath test will be considered as a measure of compliance during the wash-out days for all subjects.

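### SAP 11.4 excuses every Day 0 exhaled-CO value above 10 ppm, including the evening test 21-22.5 h after the last permitted cigarette, so the Day 1 pre-T0 test is the only scored CO check of the first wash-out

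*SAP*

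**What the plan says.** Protocol 6.6.4 gives exhaled CO a role on both wash-out days: "Furthermore, the CO breath test will be considered as one of the measures of compliance during the wash-out days in all subjects". SAP 6.3.3 repeats it: "Furthermore, the CO breath test will be considered as a measure of compliance during the wash-out days for all subjects". SAP 11.4 opens by listing Day 0 and Day 2 as wash-out days on which CO monitors compliance.

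SAP 11.4 then sets the scoring rule at 10 ppm:

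- On single use days a value above the cut-off is non-compliance "if such values are observed prior to first product use on the single use days for all exposures", and throughout the day for NNS.
- For the second wash-out day the rule is strict: "During the washout days values above 10 ppm will be considered non-compliance on Day 2".
- For the first wash-out day a value over the cut-off is excused, by the clause "but will be expected on Day 0 because smoking is ad libitum during Day -1".

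The last clause does not distinguish between the four Day 0 tests, which SAP 11.6.2.2.1 schedules at 8:00-9:30 AM, 12:00-1:30 PM, 4:00-5:30 PM and 8:00-9:30 PM. Under protocol 6.3.2, "each subject will maintain nicotine abstinence from Day -1 at 11:00 PM to the time of single use" of the allocated product on Day 1.

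SAP section 9, which lists changes from the protocol analysis, does not mention the waiver. SAP Table 10 makes nicotine or tobacco use on wash-out days a major deviation and points to Section 11.4 as an example of how it is identified. Table 15.2.5.1 tabulates non-compliant subjects by study day.

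**The concern.** The reason given for the waiver is carry-over from permitted smoking on Day -1. That is a fair reason early on Day 0, but it weakens with every hour and is least convincing in the evening. As written, no Day 0 reading can be scored as non-compliance, however late or high it is, although three places in the two documents name CO as a compliance measure for that day.

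What is at stake is classification and interpretation. The rule feeds the major-deviation category and the compliance table. It also bears on an event that has already occurred: SAP 3.1 records that "For a number of subjects the nicotine concentrations at" T0 were higher than expected, and version 3.0 responded by keeping all subjects in the primary analysis whatever their T0 value. A scored late Day 0 CO value is existing evidence that could help to separate undeclared smoking from other explanations for those concentrations.

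**Working it through.** The plan states no figure to reproduce here. The check is clock arithmetic plus first-order decay.

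**Inputs from the documents**

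- Last permitted smoking: 11:00 PM on Day -1 (protocol 6.3.1, 6.3.2 and Table 5).
- Day 0 CO test windows: as above (SAP 11.6.2.2.1; protocol Table 6).
- Day 1 pre-T0 test: within 15 minutes before T0, with T0 between 6:00 and 9:00 AM, so 5:45 to 9:00 AM.
- Cut-off: 10 ppm (SAP 6.3.3).

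SAP 6.1.1 starts the first wash-out at 06:30 AM on Day 0, whereas the protocol starts abstinence at 11:00 PM on Day -1. The protocol time is used here, and it agrees with the SAP's own reference to Day -1 smoking. The two passages should be reconciled.

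**Assumption.** The documents give no CO half-life. A range of 3 to 8 h is assumed, and endogenous CO is ignored.

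**Step 1: hours since the last permitted cigarette**

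| Test | Hours after 11:00 PM, Day -1 |
|---|---|
| Day 0, 8:00-9:30 AM | 9-10.5 |
| Day 0, 12:00-1:30 PM | 13-14.5 |
| Day 0, 4:00-5:30 PM | 17-18.5 |
| Day 0, 8:00-9:30 PM | 21-22.5 |
| Day 1, pre-T0 | 30.75-34 |

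The gap from the evening test to the pre-T0 test is shortest from 9:30 PM to 5:45 AM (8.25 h) and longest from 8:00 PM to 9:00 AM (13 h).

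**Step 2: the 11 PM value needed to exceed 10 ppm with no new smoking.** Required value = 10 × 2^(t / half-life), in ppm, at the start of each window:

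| t | 3 h | 4 h | 6 h | 8 h |
|---|---|---|---|---|
| 9 h | 80 | 48 | 28 | 22 |
| 13 h | 202 | 95 | 45 | 31 |
| 17 h | 508 | 190 | 71 | 44 |
| 21 h | 1280 | 381 | 113 | 62 |

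For example, at 21 h with a 6 h half-life: 10 × 2^(21/6) = 10 × 2^3.5 = 113 ppm. Carry-over can plausibly explain a morning value. For the evening value it requires a high 11 PM value even at the longest assumed half-life.

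**Step 3: sensitivity of the check that remains.** Take an undeclared cigarette at noon on Day 0. The peak it must produce to be flagged is 10 × 2^(18 / half-life) at 6:00 AM on Day 1, and 10 × 2^(8 / half-life) at 8:00 PM on Day 0:

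| Test | 3 h | 4 h | 6 h | 8 h |
|---|---|---|---|---|
| 8:00 PM, Day 0 (waived) | 63 | 40 | 25 | 20 |
| 6:00 AM, Day 1 (scored) | 640 | 226 | 80 | 48 |

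The waived test is the more sensitive of the two for daytime smoking, by a factor of 2^(10 / half-life): about 10 at 3 h and 2.4 at 8 h.

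**Step 4: nicotine left at T0.** Protocol 4.2 puts the nicotine half-life at around 2 h. From a noon cigarette to a 6:00 AM T0 is 18 h, or 9 half-lives, leaving 0.5^9, about 0.2%. From 8:00 PM it is 10 h, or 5 half-lives, leaving 0.5^5, about 3%.

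**The case against.** A reader might infer that the first wash-out has no biochemical check, or that its CO record is thrown away. Neither is so. The Day 1 pre-T0 test closes that wash-out and is scored for every product. Day 0 values are still listed, summarised and split at 10 ppm (Tables 15.2.4.11.1 and 15.2.4.11.2, Listing 15.3.3.5). The blind review of CO data is not confined to Day 2, and SAP 10.3.1 leaves the list of major deviations open. Reviewers can see a suspicious Day 0 series and act on it. CO is also only one of several controls: subjects are confined, products are dispensed individually and butts are returned.

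A reader might also infer that the primary ratio is biased. The documents do not support that. By Step 4, the smoking that the evening test is best placed to catch leaves little nicotine at T0. T0 nicotine is measured directly, and SAP 11.6.3 plans a supportive analysis that excludes subjects whose T0 exceeds 5% of Cmax. SAP 3.1 says neither that the high T0 values arose in Period 1 nor what caused them.

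The decay argument also depends on an assumed half-life. If starting values of 22 to 80 ppm are accepted as plausible at 9 h, the 62 ppm needed at 21 h with an 8 h half-life lies within the same range. At half-lives of 6 and 8 h, so do the noon (45 and 31 ppm) and 4 PM (71 and 44 ppm) values. The calculation therefore gives no firm ground for ending the waiver after the morning test, and an evening value above 10 ppm is not proof of smoking.

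Day 2 is not an exact parallel either, since it follows one product use rather than a day of unrestricted smoking.

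These points limit the consequence and shape the remedy. They do not explain why an evening value should be called expected, and they do not remove the contradiction between the passages. Discretion at data review is also not the same as a stated rule: under the current wording, an evening value above the cut-off does not enter the non-compliance count.

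**Conclusion.** The point stands as an inconsistency worth correcting. The whole-day waiver conflicts with the Day 0 bullet in SAP 11.4, with SAP 6.3.3 and with protocol 6.6.4. Its stated reason fits the 8:00-9:30 PM test poorly: the 11 PM value would have to exceed about 62, 113, 381 or 1280 ppm at assumed half-lives of 8, 6, 4 or 3 h. The first wash-out keeps one scored CO test, which is weaker for daytime smoking than the test waived. The check is weakened, not removed.

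The consequence is confined to deviation classification, Table 15.2.5.1 and interpretation of the higher-than-expected T0 nicotine. No bias in the THS 2.2 Menthol:mCC ratio is shown. The contradiction and the 21 to 22.5 h interval come directly from the documents. The ppm figures depend on the assumed half-life range.

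**What to change.** In SAP 11.4:

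- Restrict the Day 0 waiver to the three tests before the evening one.
- Count a value above 10 ppm at the 8:00-9:30 PM test as suspected non-compliance, refer it to the pre-analysis blind data review and include it in Table 15.2.5.1.
- Flag for that review only, without automatic non-compliance, any Day 0 value above 10 ppm that is higher than the previous Day 0 value. Allow for device error, because a small rise can be measurement noise. The documents give no figure for that error, so the sponsor should set the allowance before the review.

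Under this rule every Day 0 value above 10 ppm has a defined status: waived, flagged for review or suspected non-compliance. The cost is a short edit to one paragraph. All the data are already collected. The downside is a few more subjects to discuss at data review.
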